Complete survey for self	xxx (xx.x%)
Complete survey for child	xxx (xx.x%)
(missing)	xxx (xx.x%)
Race^c	
White	xxx (xx.x%)
Black or African American	xxx (xx.x%)
American Indian or Alaska Native	xxx (xx.x%)
Asian (including South Asian and Asian Indian)	xxx (xx.x%)
Native Hawaiian or Pacific Islander	xxx (xx.x%)
Some other race	xxx (xx.x%)
(missing)	xxx (xx.x%)
Ethnicity	
Hispanic	xxx (xx.x%)
(missing)	xxx (xx.x%)
Main Reason for testing	
I wanted to be sure I/my child did not have COVID-19 before being around others	xxx (xx.x%)
I/my child had COVID-19 like symptoms	xxx (xx.x%)
I/my child was in close contact with someone who might have COVID-19	xxx (xx.x%)
I/my child was in close contact with someone who tested positive for COVID-19	xxx (xx.x%)
Someone in my household might have COVID-19	xxx (xx.x%)
Someone in my household tested positive for COVID-19	xxx (xx.x%)
Other	xxx (xx.x%)
(missing)	xxx (xx.x%)
COVID-19 test result	
Positive	xxx (xx.x%)
Negative	xxx (xx.x%)
(missing)	xxx (xx.x%)

Receive at least one dose of a COVID-19 vaccine	xxx (xx.x%)
(missing)	xxx (xx.x%)
Likelihood of future COVID-19 vaccine	
Very likely	xxx (xx.x%)
Somewhat likely	xxx (xx.x%)
Not very likely	xxx (xx.x%)
Not at all likely	xxx (xx.x%)
(missing)	xxx (xx.x%)
Easiest way to get free COVID-19 oral medications	
An urgent care center	xxx (xx.x%)
A doctor's or other health professional's office	xxx (xx.x%)
A mobile health unit	xxx (xx.x%)
A drug store/pharmacy	xxx (xx.x%)
A grocery store	xxx (xx.x%)
A community center	xxx (xx.x%)
A place of worship	xxx (xx.x%)
A community park	xxx (xx.x%)
A neighborhood school	xxx (xx.x%)
Other	xxx (xx.x%)
(missing)	xxx (xx.x%)

Note:

- a. The total entries reflect number of entries in Front Door Survey that have a valid SARS CoV-2 test response (i.e., positive or negative).
- b. Age Category is based on participant's response on the question *I am completing this survey for* each entry. If participants chose *Myself* or *Another household member* in their entries, they presumably were Adult; likewise, if *A child* were chosen in their entries, the participants presumably were children. However, there is no guarantee that *Myself* or *Another household member* is an adult, or *A child* is a child. No other valid information can be linked with Front Door Survey to identify the actual age category.
- c. Participants could check all Race that apply.

Table 6. Regression estimates for the association between sociodemographic factors and COVID-19 testing, vaccination, and medication outcomes

	Reason for test use						Test result		Vaccination status				Perceived easiest place to access COVID-19 oral medications	
	Close contact possible COVID-19 (N= xxx)	Close contact COVID-19 positive (N= xxx)	Household member COVID-19 positive (N= xxx)	Positive COVID-19 test result (N= xxx)		Received at least one vaccine dose (N= xxx)	Likelihood of future vaccination ^a (N= xxx)	Pharmacy only vs. doctor's office or community setting ^b (N= xxx)						
All Respondents ^e (N= xxx)	OR _{Adj} ^c	95% CI	OR _{Adj} ^c	95% CI	OR _{Adj} ^c	95% CI	OR _{Adj} ^c	95% CI	OR _{Adj} ^d	95% CI	OR _{Adj} ^d	95% CI		
Age, years														
<18	X.X	X.X - X.X	X.X	X.X - X.X	X.X	X.X - X.X	X.X	X.X - X.X	X.X	X.X - X.X	X.X	X.X	X.X - X.X	
≥18	
Race														
Black	X.X	X.X - X.X	X.X	X.X - X.X	X.X	X.X - X.X	X.X	X.X - X.X	X.X	X.X - X.X	X.X	X.X	X.X - X.X	
Other	X.X	X.X - X.X	X.X	X.X - X.X	X.X	X.X - X.X	X.X	X.X - X.X	X.X	X.X - X.X	X.X	X.X	X.X - X.X	
Asian	X.X	X.X - X.X	X.X	X.X - X.X	X.X	X.X - X.X	X.X	X.X - X.X	X.X	X.X - X.X	X.X	X.X	X.X - X.X	
Multiple	X.X	X.X - X.X	X.X	X.X - X.X	X.X	X.X - X.X	X.X	X.X - X.X	X.X	X.X - X.X	X.X	X.X	X.X - X.X	
White	
Ethnicity														
Hispanic/Latino/ Spanish	X.X	X.X - X.X	X.X	X.X - X.X	X.X	X.X - X.X	X.X	X.X - X.X	X.X	X.X - X.X	X.X	X.X	X.X - X.X	
Non-Hispanic/Latino/ Spanish	

Language														
English	x.x	x.x - x.x												
Spanish

Note:

NA=odds ratio not estimable due to small sample sizes.

Bolded estimates p<.05.

^aLikelihood of future vaccination per one unit change (Not at all likely to not very likely; Not very likely to somewhat likely; Somewhat likely to very likely).

^bCommunity settings=grocery store, community center, place of worship, community park, neighborhood school, or other.

^cEstimates based on binary logistic regression, adjusted for age, race, and ethnicity.

^dEstimates based ordinal logistic regression, adjusted for age, race, and ethnicity.

^eNumber of All respondents is the number of participants who have complete data on full set of sociodemographic factors (i.e., Age, Race, Ethnicity, and Language), sample size on each outcome could vary based on the number of participants respond to the relevant survey item.

Table 7. Regression estimates for the association between social determinants of health and COVID-19 testing attitude and behavior in Baseline Survey

	Easy to get tested for COVID-19 ^a (N= xxx)		Has been tested for COVID-19 (N= xxx)	
	OR _{Adj} ^b	95% CI	OR _{Adj} ^c	95% CI
All Respondents^d (N= xxx)				
Gender Identify				
Woman	X.X	X.X - X.X	X.X	X.X - X.X
Man	X.X	X.X - X.X	X.X	X.X - X.X
Non-binary	X.X	X.X - X.X	X.X	X.X - X.X
Transgender man	X.X	X.X - X.X	X.X	X.X - X.X
Transgender woman	X.X	X.X - X.X	X.X	X.X - X.X
Gender nonconforming	X.X	X.X - X.X	X.X	X.X - X.X
Agender	X.X	X.X - X.X	X.X	X.X - X.X
Bigender
Transitional Housing/Shelter/Homelessness	X.X	X.X - X.X	X.X	X.X - X.X
Congregate Housing				
Group care setting	X.X	X.X - X.X	X.X	X.X - X.X
Nursing home	X.X	X.X - X.X	X.X	X.X - X.X
Residential care facility for disabled people	X.X	X.X - X.X	X.X	X.X - X.X
Psychiatric treatment facility	X.X	X.X - X.X	X.X	X.X - X.X
Group home	X.X	X.X - X.X	X.X	X.X - X.X
Board and care home	X.X	X.X - X.X	X.X	X.X - X.X
Prison or jail	X.X	X.X - X.X	X.X	X.X - X.X
Halfway house	X.X	X.X - X.X	X.X	X.X - X.X
Foster care	X.X	X.X - X.X	X.X	X.X - X.X
Homeless or in no consistent shelter

Loss of Employment due to COVID-19	X.X	X.X - X.X	X.X	X.X - X.X
Current employment status				
Working now	X.X	X.X - X.X	X.X	X.X - X.X
Temporarily laid off/sick leave/maternity leave	X.X	X.X - X.X	X.X	X.X - X.X
Unemployed	X.X	X.X - X.X	X.X	X.X - X.X
Retired	X.X	X.X - X.X	X.X	X.X - X.X
Permanently/temporarily disabled	X.X	X.X - X.X	X.X	X.X - X.X
Keeping house	X.X	X.X - X.X	X.X	X.X - X.X
Student	X.X	X.X - X.X	X.X	X.X - X.X
Other
Health Insurance				
No health insurance	X.X	X.X - X.X	X.X	X.X - X.X
Private insurance	X.X	X.X - X.X	X.X	X.X - X.X
Public insurance (Medicare/Medicaid/Tricare)
Loss Health Coverage due to COVID-19 Pandemic	X.X	X.X - X.X	X.X	X.X - X.X
Getting the Needed Health Care during COVID-19 Pandemic				
No, not a challenge	X.X	X.X - X.X	X.X	X.X - X.X
Yes, a minor challenge	X.X	X.X - X.X	X.X	X.X - X.X
Yes, this is a major challenge
Have A Place to Stay/Live during COVID-19 Pandemic				
No, not a challenge	X.X	X.X - X.X	X.X	X.X - X.X
Yes, a minor challenge	X.X	X.X - X.X	X.X	X.X - X.X
Yes, this is a major challenge
Getting Enough Food to Eat during COVID-19 Pandemic				
No, not a challenge	X.X	X.X - X.X	X.X	X.X - X.X

Yes, a minor challenge	X.X	X.X - X.X	X.X	X.X - X.X
Yes, this is a major challenge
Having Clean Water to Drink during COVID-19 Pandemic				
No, not a challenge	X.X	X.X - X.X	X.X	X.X - X.X
Yes, a minor challenge	X.X	X.X - X.X	X.X	X.X - X.X
Yes, this is a major challenge
Getting the Needed Medicine during COVID-19 Pandemic				
No, not a challenge	X.X	X.X - X.X	X.X	X.X - X.X
Yes, a minor challenge	X.X	X.X - X.X	X.X	X.X - X.X
Yes, this is a major challenge
Getting to Needed-to-Go Place during COVID-19 Pandemic				
No, not a challenge	X.X	X.X - X.X	X.X	X.X - X.X
Yes, a minor challenge	X.X	X.X - X.X	X.X	X.X - X.X
Yes, this is a major challenge

Note:

NA=odds ratio not estimable due to small sample sizes.

Bolded estimates p<.05.

^aEasy to get tested for COVID-19^a per one unit change (Strongly disagree to Disagree, Disagree to Neither disagree or agree; Neither disagree or agree to Agree; Agree to Strongly agree).

^bEstimates based on ordinal logistic regression, adjusted for gender identity.

^cEstimates based on binary logistic regression, adjusted for gender identity.

^dNumber of All respondents is the number of participants who have complete data on full set of social determinants of health factors (i.e., gender identity, food/water/housing insecurity, employment, and health insurance), sample size on each outcome could vary based on the number of participants respond to the relevant survey item.

History of Changes to this Document

Version	Date	Description of Change(s)
1.0	03 March 2022	Initial draft
2.0	30 April 2022	Revision based on PIs' comments

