A participant could scan a QR code on the participant instruction card or the You & Me COVID-Free bag to access a 1-minute Front Door Survey each time she/he takes a swab test. Individuals will also be invited to complete a more detailed Baseline Survey, which will take about 20 minutes, and then another short follow-up survey (i.e., End of Study Survey) about four weeks later. There is no consent required for each completion of the Front Door Survey and scanning the QR code will start the Front Door Survey automatically. Immediately following the Front Door Survey, the participant is asked if they would like to participate in the sub study. If they agree, they are asked to sign an informed consent form and then given the Baseline Survey to complete. The End of Study Survey is administered 28 days following the completion of the Baseline Survey. The participants who fill out the Baseline Survey and the End of Study Survey will be included in the sub study if they provide a signed and dated informed consent form. There are no exclusion criteria.

As the at-home tests are authorized for children ages 2 and up, these children may also participate in at-home testing, but they will not be enrolled as participants themselves. For children 2 to 14 years of age, an adult must collect the sample and complete the test procedure. Data will be obtained from participants at the individual level.

The Front Door Survey is administered after each swab test by scanning the QR code. There is no consent needed for the Front Door Survey. Immediately following the Front Door Survey, the Baseline Survey is administered at the time of informed consent. The End of Study Survey is administered 28 days following the completion of the Baseline Survey.

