Among 1,208 consented participants in Baseline Survey, no participant completed full set of secondary outcomes, 1,208 participants partially completed secondary outcomes, and no participant were missing all secondary outcomes. See details in Table 2.

Table 2. Missingness of Secondary Outcomes in Baseline Survey

[figure not shown]
	Participant attitudes towards SARS-CoV-2 vaccination		Accessibility to personal protective equipment and distancing in the work place			Self-report COVID-19 testing				Self-report symptoms
	Reasons for getting COVID vaccine	Reasons for not getting COVID vaccine	Have access to necessary facilities to wash	Work require to be in close contact with others	have access to necessary personal protective equipment	Testing method	Have been tested for COVID	Have tested positive for COVID	Accessibility to testing	12 survey items
Missing	0	0	642	643	642	375	216	376	218	275-381
Not missing	1208	1208	566	565	566	833	992	832	990	827-933
Total	1208	1208	1208	1208	1208	1208	1208	1208	1208	1208

Figure 1. Consort Diagram of Front Door Survey and Baseline Survey

Front Door Survey

Baseline Survey

Participants for this sub-study will be recruited within Merced County, California, participating in the larger public health intervention. Recruitment strategies include marketing with public health messaging in collaboration with local health departments, community organizations, media and targeted social media outreach for awareness and education, as well as other strategies that would be tailored to the different distribution scenarios. Participants may be compensated up to \$50 for completion of all surveys. The sample size is up to 300,000 for the sub-study. The test kits distributed as part of the larger study will contain information about the sub-study and how-to consent using either a mobile application (e-consent) accessible free of charge to participants or via phone consenting (verbal consent).

All analyses will be conducted in the evaluable populations corresponding to the Front Door Survey and the Baseline Survey. The Front Door Survey Evaluable Population is defined as entries that have a valid SARS CoV-2 test response (i.e., positive or negative). The Baseline Survey Evaluable Population is defined as participants who were 2 years of age or above at enrollment, consenting to participate in the Baseline and End of Study Surveys.

Intervention

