6. Objective: Model the association between social determinants of health (i.e., gender identity, employment, food/water/housing insecurity, and health insurance) and the following outcomes in the Baseline Survey Evaluable Population

- i) testing attitude (i.e., Participant thinks it's easy to get tested for COVID-19)
- ii) testing behavior (i.e., Participant has been tested for COVID-19)

Analysis: Social determinants of health and outcomes will be drawn from the Baseline Survey. For the outcome i) testing attitudes (i.e., Participant thinks it's easy to get tested for COVID-19), ordinal logistic regression will be used. For the outcome ii) testing behavior (i.e., Participant has been tested for COVID-19), logistic regression will be used. Odds ratio estimates and 95% confidence interval will be presented in Table 7.

The methods described above will constitute the main analysis of these secondary outcomes. The hypothesis is defined as:

$$H_0: \beta_i = 0$$

$$H_a: \beta_i \neq 0$$

And the logit is the linear function: $\ln(\frac{P}{1-P}) = \alpha + \beta_1x_1 + \beta_2x_2 + \dots + \beta_kx_k$

Where β_i is the parameter coefficient of independent variable x_i , and p represents the true probability that the dependent variable $y=1$ (event) given the numeric values on the independent variables. This analysis will be conducted using PROC LOGISTIC in SAS. The hypothesis as expressed above will be tested at a 2-sided significance level of 0.05

- See Appendix for proposed:
 - o Table 7: Regression estimates for the association between social determinants of health and COVID-19 testing attitude and behavior

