APPENDIX I - Proposed Table and Figure Listing

Table 1. Participant Sociodemographic Characteristics and Medical History in Baseline Survey in Merced County, CA

Characteristic	Minor (N=xxx)	Adult (N=xxx)	All Respondents (N=xxx) ^a
Age			
Median age in years	xx.x	xx.x	xx.x
(Missing)	xxx (xx.x%)	xxx (xx.x%)	xxx (xx.x%)
Race^b			
White	xxx (xx.x%)	xxx (xx.x%)	xxx (xx.x%)
Black or African American	xxx (xx.x%)	xxx (xx.x%)	xxx (xx.x%)
American Indian or Alaska Native	xxx (xx.x%)	xxx (xx.x%)	xxx (xx.x%)
Asian (including South Asian and Asian Indian)	xxx (xx.x%)	xxx (xx.x%)	xxx (xx.x%)
Native Hawaiian or Pacific Islander	xxx (xx.x%)	xxx (xx.x%)	xxx (xx.x%)
Some other race	xxx (xx.x%)	xxx (xx.x%)	xxx (xx.x%)
(Missing)	xxx (xx.x%)	xxx (xx.x%)	xxx (xx.x%)
Ethnicity			
Hispanic	xxx (xx.x%)	xxx (xx.x%)	xxx (xx.x%)
(Missing)	xxx (xx.x%)	xxx (xx.x%)	xxx (xx.x%)
Gender Identify			
Woman	xxx (xx.x%)	xxx (xx.x%)	xxx (xx.x%)
Man	xxx (xx.x%)	xxx (xx.x%)	xxx (xx.x%)
Non-binary	xxx (xx.x%)	xxx (xx.x%)	xxx (xx.x%)
Transgender man	xxx (xx.x%)	xxx (xx.x%)	xxx (xx.x%)
Transgender woman	xxx (xx.x%)	xxx (xx.x%)	xxx (xx.x%)
Gender nonconforming	xxx (xx.x%)	xxx (xx.x%)	xxx (xx.x%)
Agender	xxx (xx.x%)	xxx (xx.x%)	xxx (xx.x%)
Bigender	xxx (xx.x%)	xxx (xx.x%)	xxx (xx.x%)
(Missing)	xxx (xx.x%)	xxx (xx.x%)	xxx (xx.x%)
Current Pregnancy^c	N/A	xxx (xx.x%)	xxx (xx.x%)
(Missing)	N/A	xxx (xx.x%)	xxx (xx.x%)
Education			

Have never gone to school	xxx (xx.x%)	xxx (xx.x%)	xxx (xx.x%)
Completed 5 th grade or less	xxx (xx.x%)	xxx (xx.x%)	xxx (xx.x%)
Completed 6 th to 8 th grade	xxx (xx.x%)	xxx (xx.x%)	xxx (xx.x%)
Completed 9 th to 12 th grade	xxx (xx.x%)	xxx (xx.x%)	xxx (xx.x%)
Completed High school graduate or GED	xxx (xx.x%)	xxx (xx.x%)	xxx (xx.x%)
Completed Some college level/Technical/Vocational	xxx (xx.x%)	xxx (xx.x%)	xxx (xx.x%)
Completed Bachelor's degree	xxx (xx.x%)	xxx (xx.x%)	xxx (xx.x%)
Completed Master's/Doctoral degree	xxx (xx.x%)	xxx (xx.x%)	xxx (xx.x%)
(Missing)	xxx (xx.x%)	xxx (xx.x%)	xxx (xx.x%)
Household Member			
Just me	xxx (xx.x%)	xxx (xx.x%)	xxx (xx.x%)
Living with spouse, no kids	xxx (xx.x%)	xxx (xx.x%)	xxx (xx.x%)
Family including kids	xxx (xx.x%)	xxx (xx.x%)	xxx (xx.x%)
Family with 3 generations	xxx (xx.x%)	xxx (xx.x%)	xxx (xx.x%)
Family with 4 generations	xxx (xx.x%)	xxx (xx.x%)	xxx (xx.x%)
Living with roommates	xxx (xx.x%)	xxx (xx.x%)	xxx (xx.x%)
(Missing)	xxx (xx.x%)	xxx (xx.x%)	xxx (xx.x%)
Transitional Housing/Shelter/Homelessness			

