(Missing)	xxx (xx.x%)	xxx (xx.x%)	xxx (xx.x%)
Congregate Housing			
Group care setting	xxx (xx.x%)	xxx (xx.x%)	xxx (xx.x%)
Nursing home	xxx (xx.x%)	xxx (xx.x%)	xxx (xx.x%)
Residential care facility for disabled people	xxx (xx.x%)	xxx (xx.x%)	xxx (xx.x%)
Psychiatric treatment facility	xxx (xx.x%)	xxx (xx.x%)	xxx (xx.x%)
Group home	xxx (xx.x%)	xxx (xx.x%)	xxx (xx.x%)
Board and care home	xxx (xx.x%)	xxx (xx.x%)	xxx (xx.x%)
Prison or jail	xxx (xx.x%)	xxx (xx.x%)	xxx (xx.x%)
Halfway house	xxx (xx.x%)	xxx (xx.x%)	xxx (xx.x%)
Foster care	xxx (xx.x%)	xxx (xx.x%)	xxx (xx.x%)
Homeless or in no consistent shelter	xxx (xx.x%)	xxx (xx.x%)	xxx (xx.x%)
(Missing)	xxx (xx.x%)	xxx (xx.x%)	xxx (xx.x%)

Loss of Employment due to COVID-19	xxx (xx.x%)	xxx (xx.x%)	xxx (xx.x%)
(Missing)	xxx (xx.x%)	xxx (xx.x%)	xxx (xx.x%)
Current employment status			
Working now	N/A	xxx (xx.x%)	xxx (xx.x%)
Temporarily laid off/sick leave/maternity leave	N/A	xxx (xx.x%)	xxx (xx.x%)
Unemployed	N/A	xxx (xx.x%)	xxx (xx.x%)
Retired	N/A	xxx (xx.x%)	xxx (xx.x%)
Permanently/temporarily disabled	N/A	xxx (xx.x%)	xxx (xx.x%)
Keeping house	N/A	xxx (xx.x%)	xxx (xx.x%)
Student	xxx (xx.x%)	xxx (xx.x%)	xxx (xx.x%)
Other	xxx (xx.x%)	xxx (xx.x%)	xxx (xx.x%)
(Missing)	xxx (xx.x%)	xxx (xx.x%)	xxx (xx.x%)
Essential worker	N/A	xxx (xx.x%)	xxx (xx.x%)
(Missing)	N/A	xxx (xx.x%)	xxx (xx.x%)
Work place			
Nursing care facilities	N/A	xxx (xx.x%)	xxx (xx.x%)
Visiting nurse/home health aide service	N/A	xxx (xx.x%)	xxx (xx.x%)
Building cleaning services	N/A	xxx (xx.x%)	xxx (xx.x%)
Public transportation	N/A	xxx (xx.x%)	xxx (xx.x%)
Corrections facility	N/A	xxx (xx.x%)	xxx (xx.x%)
EMT or paramedic services	N/A	xxx (xx.x%)	xxx (xx.x%)
Meat packing farm facility	N/A	xxx (xx.x%)	xxx (xx.x%)
Agriculture and food production	N/A	xxx (xx.x%)	xxx (xx.x%)
Grocery store	N/A	xxx (xx.x%)	xxx (xx.x%)
Construction	N/A	xxx (xx.x%)	xxx (xx.x%)
(Missing)	N/A	xxx (xx.x%)	xxx (xx.x%)
Health Insurance			
No health insurance	xxx (xx.x%)	xxx (xx.x%)	xxx (xx.x%)
Private insurance	xxx (xx.x%)	xxx (xx.x%)	xxx (xx.x%)
Public insurance (Medicare/Medicaid/Tricare)	xxx (xx.x%)	xxx (xx.x%)	xxx (xx.x%)
(Missing)	xxx (xx.x%)	xxx (xx.x%)	xxx (xx.x%)

Loss Health Coverage due to COVID-19 Pandemic	xxx (xx.x%)	xxx (xx.x%)	xxx (xx.x%)
(Missing)	xxx (xx.x%)	xxx (xx.x%)	xxx (xx.x%)
Language Spoken Other than English	xxx (xx.x%)	xxx (xx.x%)	xxx (xx.x%)
(Missing)	xxx (xx.x%)	xxx (xx.x%)	xxx (xx.x%)
Family Income			

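### Table 7 (Objective 6) names no reference level and by its layout compares every gender group with Bigender; age is left out of the models, which leaves the employment odds ratios open to confounding

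*SAP*

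**What the plan says.** Objective 6 relates social determinants of health to two outcomes, finding testing easy (ordinal) and having been tested (binary): "Social determinants of health and outcomes will be drawn from the Baseline Survey". It writes a logit with k predictors, tests each coefficient at two-sided 0.05 and sends the odds ratios to Table 7, where p below .05 is bolded.

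No text or footnote names a reference level. In the Table 7 shell, each multi-level factor has placeholder estimates in every row except the last, which has dots. The dotted rows are Bigender, "Homeless or in no consistent shelter", Other (employment), public insurance, and the major-challenge answer of each challenge item. Non-estimable results have their own code: "NA=odds ratio not estimable due to small sample sizes". Single-row yes/no factors such as "Transitional Housing/Shelter/Homelessness" do carry an estimate, against a level that is not printed.

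Notes b and c say that the estimates are adjusted for gender identity. Note d counts respondents with complete data on the full set of social determinants. Age appears in none of these places, nor among the Table 7 rows. Appendix Table 1 shows that the Baseline Survey collects it ("Median age in years").

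**The concern.** **Reference levels.** A programmer who follows the shell would compare each of the seven other gender groups with Bigender. If that group is small, every gender odds ratio takes on its imprecision, including those for women and men, and the bolding tests each group against it. No interval for men against women would be printed. If nobody in the reference group is untested, all seven odds ratios for having been tested fail, and the NA note would blame small samples for what the choice of reference caused.

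**Age.** Table 7 heads its odds ratios as adjusted and includes "Current employment status", whose levels include Retired and Student. Those levels follow age closely. If testing also varies with age, the employment odds ratios carry the age difference. Table 6 does adjust for age, although the Front Door Survey has only a proxy age category. The survey that records age in years is the one left unadjusted.

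**Working it through.** **1. Are the dotted rows references?** Four features of the shells point that way:
- In Table 7 only the last row of each multi-level factor is dotted.
- NA is a separate code, so dots do not mean non-estimable.
- Table 6 dots its last rows in the same way, among them White, 18 and over, and non-Hispanic, which are natural references.
- In Table 6 White was moved to the last row (Table 5 lists it first). Table 7 keeps the Table 1 order for gender and congregate housing, so its last row is probably just the last option on the list.

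**2. How much of the table is affected?** Estimates printed per outcome: gender 7 + transitional housing 1 + congregate housing 9 + job loss 1 + employment 7 + insurance 2 + lost coverage 1 + six challenge items × 2 = 40. The gender reference governs 7 of the 40. Changing a reference only re-expresses the same fit, so joint tests and other factors' estimates stay the same.

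**3. Precision against a small reference.** The plan gives no figure to reproduce. Group sizes are assumptions. The tested share p is inferred from SAP Table 2 (Missingness), with 992 non-missing on ever tested and 833 on testing method. If only tested people were asked the method, p = 833/992 = 0.84. The range used is 0.75 to 0.95.

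Binary outcome, same p in both groups: 95% CI factor = exp{1.96 × √[1/(n_ref p(1−p)) + 1/(600 p(1−p))]}. For n_ref = 5 and p = 0.84 (unrounded p(1−p) = 0.1346): √(1.486 + 0.012) = 1.224, and exp(1.96 × 1.224) = 11.0.

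| Comparison | p = 0.75 | p = 0.84 | p = 0.95 |
|---|---|---|---|
| 600 women vs reference of 5 | 7.6 | 11.0 | 57 |
| vs reference of 10 | 4.2 | 5.5 | 18 |
| vs reference of 20 | 2.8 | 3.4 | 7.7 |
| 300 men vs 600 women | 1.38 | 1.46 | 1.89 |

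Chance that the reference has no untested person = p^n_ref:

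| n_ref | p = 0.75 | p = 0.84 | p = 0.95 |
|---|---|---|---|
| 5 | 24% | 42% | 77% |
| 10 | 6% | 17% | 60% |
| 20 | 0.3% | 3% | 36% |

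Ordinal outcome, proportional-odds approximation with five equal categories: SE = √[3(1/n₁ + 1/n₂)/(1 − Σp³)], where Σp³ = 5 × 0.2³ = 0.04. The factors are 4.7, 3.0 and 2.2 for references of 5, 10 and 20, against 1.28 for 300 vs 600.

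**4. Is age in the model?** The k-predictor logit and note d point to one joint model. Notes b and c point to one factor plus gender identity. Age is absent under both readings.

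**5. What could omitting age do?** Assume employment has no effect, 90% of Retired and 5% of Working now are 65 or over, under-65s are 86% tested, and those 65 and over are tested with share q. Then Working now = 0.95 × 0.86 + 0.05q and Retired = 0.10 × 0.86 + 0.90q. At q = 0.76 these are 0.855 and 0.770, so the odds ratio for Retired vs Working now is (0.770/0.230)/(0.855/0.145) = 0.57.

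| q | 0.76 | 0.81 | 0.86 | 0.90 |
|---|---|---|---|---|
| OR, no true effect | 0.57 | 0.73 | 1.00 | 1.38 |

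With 70% and 10% aged 65 or over instead, the values are 0.66, 0.80, 1.00 and 1.25.

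**The case against.** The appendix is a list of proposed shells, and nothing says that dots mark a reference. Spanish is also dotted in Table 6 and is not an obvious baseline. Last-on-the-list rows fit an unfinished placeholder as well as a deliberate choice. This stands to the extent that the reference status is apparent, not stated; the plain fact is that no reference is named.

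The loss is also limited. Rare levels stay imprecise under any reference, and when the fit is finite one extra contrast gives men against women. That is true, but the plan does not ask for that contrast.

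A reader might infer from the shell that people in ordinary housing drop out of the congregate-housing factor, or that homeless respondents are certainly its baseline. The documents do not support either. The survey coding is not given, and an unprinted level may be a shell convention, since Table 1 prints only Hispanic under ethnicity. The yes/no rows carry an estimate while "Homeless or in no consistent shelter" does not, so the row reads as the reference, but that is all that can be said.

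The age effect is hypothetical. Every input in step 5 is assumed, and the result passes through 1.00. That stands too: the documents show that age is omitted, not that bias follows. These are also secondary outcomes under an exploratory aim. However, the SAP calls this their main analysis and tests each coefficient, so readers will interpret the bolded results.

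**Conclusion.** The point holds in two parts. First, Table 7 names no reference level, and its layout makes Bigender the apparent one for gender identity. If that group is as small as 5 to 20 people, the seven gender odds ratios would be several times less precise than a comparison of common levels, and those for having been tested may not be estimable at all. Sparsity is likely but not shown, and the figures rest on assumed group sizes and an inferred tested share. Second, age is missing from the Objective 6 models under either reading, so the employment odds ratios are open to confounding by age, with direction and size unknown.

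A reader might go further and infer that leaving out race and ethnicity is an error of the same kind, because Table 6 includes them. The documents do not support that. Whether to hold race and ethnicity fixed when describing social determinants is a choice of estimand, and no mechanism comparable to age and employment is evident. Adjusting for them would be an optional sensitivity analysis.

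This is worth fixing because it is cheap and changes what Table 7 can show. It does not call the other planned analyses into question.

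**What to change.** In Objective 6 and Table 7:

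- **References.** Name a reference for every factor and set it to a common level confirmed from the Table 1 counts, for example Woman or Man for gender identity.
- **Pooling.** Combine sparse levels under a stated minimum count. For the five-category ordinal outcome, set the minimum per level overall, because 5 people in each category would need at least 5 × 5 = 25 per level.
- **Age.** Add age in years, at least to the employment model, with the linearity check and splines already planned under Objective 5.
- **Congregate housing.** If the coding identifies people not in congregate housing, make them the reference or use a yes/no variable. Otherwise report the factor descriptively.
- **Model form.** State whether models are joint or one factor at a time, and align notes b, c and d.

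As a separate point, the SAP must reconcile its statements on minors. Study Population says of children that "they will not be enrolled as participants themselves", while the Baseline Survey Evaluable Population is "participants who were 2 years of age or above at enrollment". This decides who enters Table 7.

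The cost is SAP wording and model code, with no new data; the congregate-housing change depends on the existing coding. The downsides are less detail on very small groups, a few more coefficients for age, and the loss of respondents with missing age.

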No imputation will be performed for missing data. Participants who *do not know* or *prefer not to answer* a question used as an outcome variable will be treated as missing data. Survey entries which do not show a valid (positive or negative) SARS CoV-2 test result (N=111) in the Front Door Survey will not be included in the Front Door Survey Evaluable Population. Out of the 2,510 entries in the Front Door Survey, 425 completed survey items on key primary outcomes. Among the 1,313 respondents who consented to participate Baseline and End of Study Survey, 480 completed survey items on key secondary outcomes.

Analysis Objectives and Tasks

- Objective:** Summarize sociodemographic characteristics and medical history of participants in the Baseline Survey Evaluable Population and summarize sociodemographic and test-relevant characteristics of entries in Front Door Survey Evaluable Population

Analysis: Sociodemographic characteristics and medical history summaries will be presented in Table 1. All the sociodemographic characteristics and medical history variables from the Baseline Survey will be summarized by age category (Adult, Minor, Overall) where Adult is defined as age ≥ 18 years of age. Similarly, sociodemographic and test-relevant characteristics of entries will be presented in Table 5. All variables are categorical and will be summarized as counts and percentages. The denominators for the percentages for each variable in Table 1 are defined as the number of participants in the Baseline Survey Evaluable Population who have non-missing data for the variable. The denominators for the percentages for each variable in Table 5 are defined as the frequency of entries in the Front Door Survey Evaluable Population which have non-missing data for the variable.

- See Appendix for proposed:
 - Table 1: Participant Sociodemographic Characteristics and Medical History in Baseline Survey in Merced County, CA
 - Table 5: Sociodemographic and Test-relevant Characteristics in Front Door Survey Entries in Merced County, CA

- Objective:** Summarize self-reported COVID-19 testing characteristics and symptoms corresponding to the Baseline Survey Evaluable Population

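### The Table 7 model for having been tested handles sparse levels only by printing NA, which selects on the outcome for levels of about 10 people or fewer; reference levels and model structure also need fixing

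*SAP*

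**What the plan says.** SAP, Analysis Objectives and Tasks, Objective 6: "For the outcome ii) testing behavior (i.e., Participant has been tested for COVID-19), logistic regression will be used". The software statement is "This analysis will be conducted using PROC LOGISTIC in SAS", with each coefficient tested at two-sided 0.05. No penalised or exact method, minimum cell size or collapsing rule is given.

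SAP, Appendix I, Table 7 lists 8 gender identities, 10 congregate settings, 8 employment states, 3 insurance types, three single-row items and six three-level challenge items. In each multi-level factor the last listed row is blank, which implies that it is the reference. For gender identity that is Bigender; for congregate housing it is the homeless level. The notes say that non-estimable odds ratios are shown as NA ("NA=odds ratio not estimable due to small sample sizes"), that estimates are adjusted for gender identity (note c), and that respondents must be complete on all the factors (note d).

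SAP, Study Population, Table 2 covers "Among 1,208 consented participants in Baseline Survey" and has a column headed "Have been tested for COVID". Its rows read "Missing 0 0 642 643 642 375 216 376 218 275-381" and "Not missing 1208 1208 566 565 566 833 992 832 990 827-933". The number who answered that they had not been tested is not stated.

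**The concern.** Untested people are the scarce outcome class, so they limit what this model can estimate. In a very small level, maximum likelihood gives a finite odds ratio only if the level has at least one tested and one untested member. Printing NA otherwise means that the outcome decides which odds ratios the reader sees. Against a large reference, small levels in which everyone was tested vanish, and those that remain lean towards less often tested. Aim 5 asks about social determinants of testing, and a reader could take that lean for a disparity in a small group. A rare reference level adds a second problem: if it has no untested member, no odds ratio for that factor can be estimated.

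**Working it through.** **1. Table 2 checks.** Missing plus answered: tested 216 + 992 = 1,208; method 375 + 833 = 1,208; tested positive 376 + 832 = 1,208. The rows are internally consistent.

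**2. Ceiling on the untested.** 992 − 833 = 159 and 992 − 832 = 160. The Appendix I shell for method of most recent test lists only sample types, so anyone giving a method had been tested. If only people reporting a test answered these two items, about 160 is a ceiling. It is not a count: the SAP says that a don't-know or prefer-not-to-answer response to "a question used as an outcome variable will be treated as missing data". Symptom items, with no evident skip rule, were answered by 827-933 people, short of 992 by 59 to 165, so ordinary non-response could produce much of the gap. Note d lowers the number in the model further. The ceiling share is 159/992 = 0.160.

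**3. Coefficients (levels minus one).** Gender 7, transitional housing 1, congregate housing 9, job loss 1, employment 7, insurance 2, coverage loss 1, six challenge items 6 × 2 = 12. The total is 40.
- One joint model: 160/40 = 4.0 untested per coefficient at most. If 50-80% are complete cases (assumed), 80-128 untested give 2.0-3.2.
- One factor at a time plus gender: 7 + 1 = 8 to 7 + 9 = 16 coefficients, so 160/8 = 20 down to 160/16 = 10.

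**4. Effect of the NA rule.** Take a level of n people and a reference of m, both with untested probability q = 0.160 (true odds ratio 1). Let U ~ Bin(n, q) and V ~ Bin(m, q). The odds ratio is printed only if 0 < U < n and 0 < V < m, and its log is ln[U/(n−U)] − ln[V/(m−V)]. I enumerated all tables and averaged the log odds ratio over the printed ones. For a single binary factor, Firth estimation adds 0.5 to each cell and keeps every table. Odds ratios are for being untested, with m = 500:

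| n | NA | Printed, geometric mean | Firth, all tables |
|---|---|---|---|
| 5 | 42% | 1.88 | 1.20 |
| 10 | 17% | 1.13 | 1.03 |
| 15 | 7% | 0.97 | 1.00 |
| 20 | 3% | 0.92 | 1.00 |

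The NA share is essentially (1−q)^n: 0.84^5 = 0.42 and 0.84^10 = 0.17. In Table 7's direction (tested), 1.88 becomes 1/1.88 = 0.53. At 10% untested a 5-person level is NA 59% of the time, and the printed mean is about 2.8.

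**5. Dependence on the reference.** Same formula, both levels rare: 5 versus 5 gives 1.00; 10 versus 10, 1.00; 10 versus 5, 0.60; 5 versus 3, 0.57. With a 5-person reference, the whole factor is non-estimable 42% of the time.

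**The case against.** - **The untested count is inferred.** This stands. A reader might take 160 as the number untested, but the documents give no such figure. It is only a conditional ceiling. A lower count makes sparsity worse, so the uncertainty does not remove the point.
- **Forty coefficients is one reading.** This stands. Note c also fits factor-by-factor models with 8-16 coefficients. That relieves the total count but not the rare levels, and gender identity with its 8 levels enters every model.
- **The direction is not fixed.** This stands. A reader might infer that printed odds ratios always make rare groups look less tested. Step 5 shows that the lean disappears or reverses when level and reference are both rare, as may be so for gender and congregate housing as laid out.
- **Printed values need not be extreme.** Against a reference at 16% untested (odds 0.16/0.84 = 0.190), one untested person in five gives (1/4)/0.190 = 1.31, and one in ten gives (1/9)/0.190 = 0.58. Intervals are reported and would be wide.
- **No general excess of false positives is shown.** At 16% untested, the share of printed odds ratios with Wald p < 0.05 under no association is 5.4% at n = 5, 3.8% at n = 10 and 3.3% at n = 15. A simulation of the 40-coefficient model with assumed level frequencies kept the error rate for the common challenge items at 5-6%.
- **The aim is exploratory.** Objective 6 concerns secondary outcomes, and the protocol calls its analysis mainly descriptive. This lowers the severity.

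**Conclusion.** The SAP needs a better rule than NA for Objective 6 ii. For levels of about 10 people or fewer set against a large reference, the rule selects on the outcome. The effect is material at 5 people (42% NA, printed geometric mean 1.88), modest at 10 (17%, 1.13) and small by 15-20. The implied rare reference levels are a separate weakness, because one reference with no untested member removes its whole factor.

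These sizes assume 16% untested and no true association. Level sizes are illustrative, because the SAP gives none. The documents do not support the stronger inferences that 160 people are known to be untested, that the bias runs one way whatever the reference, or that Table 7 will show an excess of bolded results. Severity is minor to moderate.

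**What to change.** In Objective 6 ii and the Table 7 notes:

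- Fit the binary model by Firth penalised likelihood with profile penalised-likelihood intervals, both available in PROC LOGISTIC.
- Take the most frequent level of each factor as reference.
- Replace the NA rule with collapsing based on respondent counts only, fixed without looking at the outcome. For example, merge levels with fewer than 10 respondents. The threshold is a choice; what matters is fixing it in advance.
- Code congregate housing as any versus none. Tables 1 and 7 list no such none level, so say that respondents outside congregate housing count as none and not as missing. Otherwise note d could remove most of the sample.
- State whether Table 7 comes from one joint model or from one model per factor adjusted for gender identity.
- Print the number of respondents and the number untested beside each odds ratio.

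The cost is SAP wording and a few lines of code. The estimates shrink slightly, and Table 7 loses category detail that descriptive Table 1 keeps. Firth alone leaves some bias at very small n (about 1.2 at 5 people), which is why the collapsing rule is needed as well.
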